4.6.4.3. Part 2, Arm B (Tafasitamab and Lenalidomide)

Follow the guidelines in [Section 4.6.4.2](#) for the prophylaxis, monitoring, and treatment of TLS.

4.7. Dose Modification Guidelines

Treat subjects experiencing a significant toxicity with standard medical interventions (eg, use of filgrastim to treat neutropenia, acetaminophen for fever) as appropriate. For infusion reactions/CRS and neurotoxicity management, Investigators may use their standard treatment practices, and for additional guidance, see [Section 4.6](#).

In general, if a > Grade 2 toxicity prevents dosing > 14 days and/or if 2 consecutive doses are missed (this applies to weekly and Q2W dosing), the subject may require discontinuation from the plamotamab or tafasitamab treatment. Subjects may reinitiate study drug, even after 2 or more missed consecutive doses of plamotamab or tafasitamab, if the Investigator determines that the benefit outweighs the risk and the toxicity (if applicable) can be controlled by concomitant medication or other means. Medical Monitor approval is required for delays of > 14 days and/or 2 consecutive doses.

During weekly dosing of plamotamab and/or tafasitamab, if a subject's dose is held for ≥ 7 days, it should be considered missed. During Q2W dosing of plamotamab and/or tafasitamab, if a subject's dose is held for ≥ 14 days, it should be considered missed. If a subject's dose is given out of window or delayed for safety concerns, including AEs, it is not considered a protocol deviation.

Plamotamab may be resumed after prolonged dose delay for more than one cycle for reasons other than toxicity (eg, comorbidity, pseudoprogression, or delayed response). Resuming initial treatment course may be allowed on a case-by-case basis if the Investigator and the Sponsor consider this in the best interest of the subject. As a safety measure, the dose may be lowered to the priming dose for re-titration. Study assessments, including local and/or central labs, are to be collected per the Schedule of Assessments.

For toxicities that could overlap (eg, CRS, infusion reaction, hematologic toxicities), detailed dose modifications by grade are presented in [Table 8](#) below:

Table 8: Dose Modifications for Select Toxicities

Adverse Reaction	Severity	Dosage Modification
Infusion-related reactions	Grade 2 (moderate)	
 • Interrupt infusion of tafasitamab or plamotamab immediately and manage signs and symptoms. • Once signs and symptoms resolve or reduce to Grade 1, resume infusion at no more than 50% of the rate at which the reaction occurred. If the subject does not experience further reaction within 1 hour and vital signs are stable, the infusion rate may be increased every 30 minutes as tolerated to the rate at which the reaction occurred. • Dosing of other study medications is not modified.
	Grade 3 (severe)	
 • Interrupt infusion of tafasitamab or plamotamab immediately and manage signs and symptoms. • Once signs and symptoms resolve or reduce to Grade 1, resume infusion at no more than 25% of the rate at which the reaction occurred. If the subject does not experience further reaction within 1 hour and vital signs are stable, the infusion rate may be increased every 30 minutes as tolerated to a maximum of 50% of the rate at which the reaction occurred. • If the reaction returns after the rechallenge, stop the infusion immediately. • Dosing of other study medications is not modified.
	Grade 4 (life-threatening)	
 • Stop the infusion immediately and permanently discontinue: 
 – Tafasitamab if during or immediately following tafasitamab infusion. – Plamotamab if during or immediately following plamotamab infusion.
Cytokine release syndrome	Grade 2 (moderate)	
 • Interrupt plamotamab infusion immediately and manage signs and symptoms (see Section 4.6.1.6). • Once signs and symptoms resolve or reduce to Grade 1, resume plamotamab infusion at no more than 50% of the rate at which the reaction occurred. If the subject does not experience further reaction within 1 hour and vital signs are stable, the infusion rate may be increased every 30 minutes as tolerated to the rate at which the reaction occurred. • Tafasitamab and lenalidomide dosing is not modified.
	Grade 3 (severe) & Grade 4 (life-threatening)	
 • Interrupt plamotamab infusion immediately and disconnect infusion tubing from subject. Manage signs and symptoms (see Section 4.6.1.6). • The next scheduled dose of plamotamab will be given at 75% of the previous dose, unless the reaction occurred

Adverse Reaction	Severity	Dosage Modification
		
on the C1D1 dose, in which case 100% of the previous dose may be given.
 
 • For subsequent plamotamab infusions, if: 
 – Toxicity does not recur or recurs at a Grade 1 severity, escalate to full dose of plamotamab at the time of the next dose. – Toxicity recurs at a Grade 2 severity, maintain 75% dosing of plamotamab. – Toxicity recurs at \geq Grade 3 severity at any time or if a Grade 2 takes more than 10 days to resolve to \leq Grade 1, discontinue plamotamab permanently. • Lenalidomide is also modified if a \geq Grade 3 CRS event occurs: 
 – During the first 5 doses of plamotamab: Reduce current dose of lenalidomide by 10 mg (or to 5 mg if currently at 10 mg) for subsequent doses until C4D1, when lenalidomide may be increased back to the dose prior to CRS. If CRS recurs at \geq Grade 2 on subsequent reduced dose lenalidomide, permanently discontinue lenalidomide. – After the first 5 doses of plamotamab: Reduce lenalidomide by 10 mg (or to 5 mg if currently at 10 mg) for all subsequent doses. If CRS recurs at \geq Grade 2 on subsequent reduced dose lenalidomide, permanently discontinue lenalidomide. • Tafasitamab dose is not modified.
Myelosuppression	Platelet count of less than 50,000/ μ L	
 • Withhold plamotamab, tafasitamab, and lenalidomide and monitor CBC weekly until platelet count is 50,000/μL or higher. • Resume plamotamab and tafasitamab at the same dose and lenalidomide at a reduced dose. Refer to lenalidomide prescribing information for dosage modifications. • If recurrence, repeat drug withholding and lenalidomide reduction steps until minimal lenalidomide dose is reached per lenalidomide prescribing information. • If recurrence at minimal lenalidomide dose, repeat drug withholding step (first bullet above) then reduce the next scheduled plamotamab dose to 75% of the previous dose.

Adverse Reaction	Severity	Dosage Modification
	
Neutrophil count of 1,000/μL or less for at least 7 days OR
 
Neutrophil count of 1,000/μL or less with an increase of body temperature to 100.4°F (38°C) or higher OR
 
Neutrophil count less than 500/μL
	
 • Withhold plamotamab, tafasitamab, and lenalidomide and monitor CBC weekly until neutrophil count is 1,000/μL or higher. • Resume plamotamab and tafasitamab at the same dose and lenalidomide at a reduced dose. Refer to lenalidomide prescribing information for dosage modifications. • If recurrence, repeat drug withholding (first bullet above) and lenalidomide reduction steps until minimal lenalidomide dose is reached per lenalidomide prescribing information. • If recurrence at 5 mg lenalidomide, repeat drug withholding steps then reduce the next scheduled plamotamab dose to 75% of the previous dose.
Febrile Neutropenia	Grade 3 (severe) & Grade 4 (life-threatening)	
 • Withhold plamotamab, tafasitamab, and lenalidomide and monitor CBC until neutrophil count is Grade \leq 1. • Once subject is afebrile, off antibiotics and neutrophil count is Grade \leq 1, resume all therapy at the same dose and schedule.
Neurotoxicity	Grade 3 (severe)	
 • Withhold plamotamab and manage signs and symptoms (see Section 4.6.1.7) until the toxicity has recovered to \leq Grade 1 (mild) and has remained at \leq Grade 1 for at least 3 days before restarting therapy. • Reduce next scheduled plamotamab dose to 75% of the previous dose. If \geq Grade 2 toxicity does not recur, escalate plamotamab to full dose in subsequent administrations. • If \geq Grade 2 toxicity recurs at 75% dose, or if $<$ Grade 2 toxicity takes more than 7 days to resolve, permanently discontinue plamotamab. • Tafasitamab and lenalidomide dosing is not modified.
	Grade 4 (life-threatening)	
 • Stop infusion immediately, if still infusing and permanently discontinue plamotamab.
AST, ALT, bilirubin, and alkaline phosphatase in the absence of CRS	Grade 3 (severe)	
 • Withhold plamotamab and manage signs and symptoms until the toxicity has recovered to \leq Grade 1 (mild) or baseline. • If a Grade 3 liver toxicity persists $>$ 14 days and/or 2 consecutive doses are missed and the toxicity cannot be attributed to another cause, permanently discontinue plamotamab. • Tafasitamab and lenalidomide dosing is not modified.
	Grade 4 (life-threatening)	
 • Withhold plamotamab, tafasitamab, and lenalidomide and manage signs and symptoms until toxicity returns to \leq Grade 1 (mild) or baseline

Adverse Reaction	Severity	Dosage Modification
		
 • If a Grade 4 liver toxicity persists > 3 days, permanently discontinue plamotamab, tafasitamab, and lenalidomide
Renal Impairment/failure	Creatinine clearance 59-30 mL/min	
 • Reduce lenalidomide to 10 mg daily on Days 1-21 of each cycle. • Tafasitamab and plamotamab dosing is not modified
	Creatinine clearance 30 mL/min not requiring dialysis	
 • Reduce lenalidomide to 15 mg every other day for Days 1-21 of each cycle. • Tafasitamab and plamotamab dosing is not modified
	Creatinine Clearance below 30 mL/min requiring dialysis	
 • Reduce lenalidomide to 5 mg once daily for Days 1-21 of each cycle. On dialysis days, administer the dose following dialysis. • Tafasitamab and plamotamab dosing is not modified

ALT = alanine aminotransferase; AST = aspartate aminotransferase; C#D#, eg C1D1 = Cycle # Day #; CBC = complete blood count; CRS = cytokine release syndrome.

For other Grade ≥ 3 AEs, other dose modifications will be considered on a case-by-case basis, after discussion between the Sponsor and Investigator.

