7. TREATMENT OF SUBJECTS

7.1. Dosing Schedule and Premedications

7.1.1. Plamotamab Dosing Schedule and Premedications

Subjects in Part 1 and those randomized to Arm A in Part 2 will be administered plamotamab IV [REDACTED] In Cycle 1, plamotamab will be administered once every 7 days (\pm 1 day) for 4 doses; beginning with Cycle 2, plamotamab will be administered every 2 weeks.

Subjects in Cohort 1A and Cohort 1B receive plamotamab according to the doses and schedule in [Table 12](#).

Table 12: Cohorts 1A and 1B Plamotamab Dosing Regimen

Cohort	Dose Level	Cycle 1 Day 1 (Priming Dose)	Cycle 1 Day 8	Cycle 1 Day 15	Cycle 1 Day 22	Cycle 2 Day 1	Cycle 2 Days 1, 8, 15, and 22	Cycle 3 and Subsequent Q2W Dosing
1A	-1	0.8 mg	2 mg	20 mg	20 mg	20 mg	20 mg	20 mg
1B	1	0.8 mg	2 mg	20 mg	35 mg	50 mg	50 mg	50 mg

Q2W = every 2 weeks.

The dose and schedule of plamotamab for Part 2 will be determined in Part 1.

Adjustments may be made to the infusion rate to increase the length of infusion time based on the Investigator's judgement of safety. Due to pump accuracy variations, infusions ending within 5 minutes prior to the required [REDACTED] period will not be considered a deviation.

Administer plamotamab at least 2 hours after tafasitamab on days when both products are given. All subjects in Part 1 and randomized to Arm A in Part 2 will be premedicated for plamotamab doses as indicated in [Table 13](#).

Table 13: Premedications for Plamotamab

	Cycle 1	Subsequent Cycles
Dexamethasone (if plamotamab alone is administered)	20 mg IV approximately 1 hour prior	Optional
Diphenhydramine	25 mg PO or IV approximately 30 to 60 minutes prior	Required
Acetaminophen	650 mg PO approximately 30 to 60 minutes prior	Required

IV = intravenous; PO = by mouth.

Subjects who have received 4 consecutive infusions at a stable dose and schedule without CRS or infusion reactions may have their premedications modified at the discretion of the Investigator.

In the event of the discontinuation of plamotamab, in the absence of disease progression, and if the subject is still receiving benefit from the study treatment, subjects may continue with other study treatment(s).

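### The protocol does not say which plamotamab dose follows a missed step-up dose; dosing by cycle day would permit a 25-fold step where the largest planned step is 10-fold

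*Protocol*

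**What the plan says.** **Schedule.** Protocol section 7.1.1 states: "Subjects in Cohort 1A and Cohort 1B receive plamotamab according to the doses and schedule in" Table 12, whose columns are cycle days (Table 3 is identical). The same section says "In Cycle 1, plamotamab will be administered once every 7 days", for four doses, so it also counts doses.

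**Missed doses.** Section 4.7 says that during weekly dosing, if a "dose is held for ≥ 7 days, it should be considered missed". It adds: "Medical Monitor approval is required for delays of > 14 days and/or 2 consecutive doses". It also says that if a "dose is given out of window or delayed for safety concerns, including AEs, it is not considered a protocol deviation". None of this names the mg dose that follows a missed step. The one re-titration sentence is permissive and belongs to a paragraph on delays of more than one cycle for reasons other than toxicity.

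**Restart dose by type of hold.**
- Grade 3 liver tests without CRS (Table 8): "Withhold plamotamab and manage signs and symptoms until the toxicity has recovered to" Grade 1 or less, or baseline. Plamotamab stops for good only if the event lasts more than "14 days and/or 2 consecutive doses are missed and the toxicity cannot be attributed to another cause, permanently discontinue plamotamab". No restart dose is given.
- Grade 4 liver tests (Table 8): "Withhold plamotamab, tafasitamab, and lenalidomide and manage signs and symptoms until toxicity returns to" Grade 1 or less, or baseline, with permanent discontinuation if the event lasts more than 3 days. No restart dose is given.
- Tumor lysis syndrome (section 4.6.4.2): treatment is held until resolution. No restart dose is given.
- Logistics or Grade 1-2 events outside the listed rows: no instruction. The case-by-case discussion after Table 8 covers only other Grade 3 or higher events.
- CRS and Grade 3 neurotoxicity: the next dose is tied to the previous one (75%, or 100% after a CRS event on C1D1). The subject then goes to *full dose*, which is not defined for the step-up period.
- Febrile neutropenia: *same dose and schedule*.
- Myelosuppression: *same dose*, which most naturally means 0.8 or 2 mg after a C1D8 hold.

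**The concern.** Section 2.4.3 says the titration was chosen to reduce the risk of CRS. The flat-dose experience cited for it is 14 subjects on a weekly titration of 0.8, 2, 20, 35 and 50 mg, with no Grade 3 or 4 CRS. The documents describe no experience with a step left out. The three-drug combination had not been given to humans (section 4.6), lenalidomide may potentiate CRS (section 4.6.1.1), and section 11.8 itself notes that CRS may be associated with longer gaps between doses. A skipped step combines a longer gap with a larger jump.

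Up to 120 sites are planned, and they cannot be expected to settle the question in the same way. CRS incidence is part of the Part 1 primary endpoint and bears on the choice between dose levels, so uneven handling of missed steps would also blur that comparison.

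**Working it through.** The protocol states no fold-step, so there is no plan figure to reproduce. The inputs are the doses in Tables 3 and 12:

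- 1A: C1D1 0.8, C1D8 2, C1D15 20 mg, then 20 mg.
- 1B: C1D1 0.8, C1D8 2, C1D15 20, C1D22 35, C2D1 50 mg, then 50 mg.

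**Step size** = next dose given / last dose given.

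Planned: 2/0.8 = 2.5; 20/2 = 10; then in 1B 35/20 = 1.75 and 50/35 = 1.43. The largest is 10.

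One dose missed:

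| Missed | Cohort | Last dose given (mg) | Next by cycle day | Next in order |
|---|---|---|---|---|
| C1D8 | 1A, 1B | 0.8 | 20 (25-fold) | 2 (2.5-fold) |
| C1D15 | 1A | 2 | 20 (10-fold) | 20 (10-fold) |
| C1D15 | 1B | 2 | 35 (17.5-fold) | 20 (10-fold) |
| C1D22 | 1B | 20 | 50 (2.5-fold) | 35 (1.75-fold) |
| C2D1 | 1B | 35 | 50 (1.43-fold) | 50 (1.43-fold) |

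In 1A, missing C1D22 or C2D1 changes nothing (20/20 = 1). Only C1D8 in both cohorts and C1D15 in 1B exceed 10-fold.

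**Approval check.** One missed weekly dose is a 7-day delay and one dose. The threshold is more than 14 days and/or 2 consecutive doses, so it is not reached.

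**The *full dose* wording.** After Grade 3 CRS on C1D1, 0.8 mg may be repeated on C1D8. If *full dose* on C1D15 is read by calendar, the step is 20/0.8 = 25-fold; in order it is 2/0.8 = 2.5-fold. The Grade 3 neurotoxicity row has the same form: 75% of 0.8 is 0.6 mg, and a calendar reading would then give 20/0.6 = 33.3-fold.

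**Plamotamab through C2D22, Cycle 2 weekly as in Table 12.**
- C1D8 missed, 1B: by cycle day 0.8 + 20 + 35 + 4×50 = 255.8 mg; in order 0.8 + 2 + 20 + 35 + 3×50 = 207.8 mg; 48.0/255.8 = 18.8% less.
- C1D8 missed, 1A: 0.8 + 6×20 = 120.8 mg against 0.8 + 2 + 5×20 = 102.8 mg; 18.0/120.8 = 14.9% less.
- C1D15 missed, 1B: 0.8 + 2 + 35 + 4×50 = 237.8 mg against 207.8 mg; 30.0/237.8 = 12.6% less.
- C1D15 missed, 1A: 102.8 mg either way.

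**The case against.** **The text leans towards dosing in order.** Section 2.4.3 describes a sequence, section 7.1.1 counts four doses, the CRS row of Table 8 counts the first five doses, and a delay for safety is not a deviation. *Full dose* most naturally means the unreduced dose; section 4.6.1.7 speaks of escalating back to it. This stands: in-order dosing is a fair reading. It still does not exclude the other one, because section 7.1.1 sends sites to a table keyed to cycle days and no sentence says that a missed step must be made up.

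**A 20 mg dose on C1D15 would be well guarded.** It would come with 20 mg IV dexamethasone, a 24-hour admission after the dose increase, scheduled cytokine samples, a physician readily available for 24 hours and tocilizumab in the immediate area. The Grade 3 CRS path also requires immediate notice to the Medical Monitor. This stands too, but these measures limit the consequences and do not set the dose.

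**Harm is inferred from a ratio.** No passage links step size to CRS risk, and the Grade 3 or higher CRS events in the NHL group all came with the first infusion (section 2.4.1). That is correct, so the size of any harm cannot be stated.

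**Frequency is unknown.** A reader might take the Grade 3/4 liver enzyme increases in the flat-dose cohort (section 2.4.3) as evidence of how often the liver route would be used. The documents do not support that. The liver rows apply only without CRS, and section 2.4.1 describes transaminase rises in the setting of CRS that usually settled within 5 days, less than the 7 that make a dose missed. Nothing shows a CRS-free liver event that led to a missed step-up dose.

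**Conclusion.** The gap is real and should be fixed. It is an ambiguity that permits calendar dosing. A reader might infer that the protocol instructs sites to skip the missed step, but the documents do not say so. Where no restart dose is set, or where *full dose* or *same dose and schedule* is read by calendar, one missed dose can lead to a 25-fold step (C1D8, both cohorts) or a 17.5-fold step (C1D15, 1B), against a planned maximum of 10-fold and with no approval required.

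This rests on the dosing tables as printed, on a single missed dose with later doses keeping their cycle day, and on no further rule in the pharmacy or study manuals, which are not among the documents. The SAP reports that the study was stopped early with 3 subjects enrolled, so the practical value now lies mainly in any reuse of this regimen.

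**What to change.** **Footnote to Tables 3 and 12:** *Step-up doses are given in order (1A: 0.8, 2, 20 mg; 1B: 0.8, 2, 20, 35, 50 mg); the days shown are the earliest days. After a missed step-up dose the missed step is given next; no step is skipped. After 2 or more consecutive missed step-up doses, the Medical Monitor approval already required also sets the restart dose, no higher than the first missed step.*

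**Table 8, events before the top dose:** define *full dose* (CRS and neurotoxicity rows) as the unreduced dose at the step where the event occurred, with the next step in order after that, so that 2 mg follows a repeated 0.8 mg. Define *same dose* as the withheld step. Apply the footnote rule to both liver rows and to tumor lysis holds.

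**Safeguards:** Cycle 1 dexamethasone, the 24-hour admission and cytokine sampling should follow any step-up dose that moves into Cycle 2. Dexamethasone is optional after Cycle 1, and C2D8 has no inpatient mark in Table 9 and no scheduled cytokines in Table 10. This matters most for a subject given 75% at the 2 mg step (1.5 mg on C1D15, 2 mg on C1D22), whose 10-fold step then falls on C2D1.

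**Cost:** text edits only, no extra subjects. After one missed C1D8 or C1D15 dose the 10-fold step falls on C1D22, still under mandatory dexamethasone. The top dose comes 7 days later than planned (1A C1D22, 1B C2D8). In 1B it is 14 days later (C2D15) if Cycle 2 is every 2 weeks, as the section 7.1.1 text reads. Through C2D22, subjects with such a miss receive 12.6% to 18.8% less plamotamab in 1B and 0% to 14.9% less in 1A than under calendar dosing. If sites may instead repeat the last tolerated dose, the protocol should say that the 10-fold step then moves to C2D1 and the top dose is 14 rather than 7 days late (Cycle 2 weekly), which makes the premedication edit essential.

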4.6.2.1. Safety Run-in and Part 2, Arm A (Plamotamab, Tafasitamab and Lenalidomide)

Infusion-related reactions have been observed with plamotamab and tafasitamab. To mitigate overlapping toxicity with plamotamab, on a given treatment day, tafasitamab must be given first with a minimum of 2 hours between the end of the tafasitamab infusion and the start of the plamotamab infusion. If a > Grade 1 infusion reaction occurs with tafasitamab, delay the plamotamab until the resolution all symptoms of the reaction. Depending on the timing of the resolution of all symptoms, it may be necessary to administer the plamotamab the following day.

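### Minor safety inconsistency: after a Grade 2 or 3 tafasitamab infusion reaction, Table 8 leaves the other drugs unmodified, while Section 4.6.2.1 delays plamotamab until all symptoms have gone

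*Protocol*

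**What the plan says.** Two parts of the protocol tell the site what to do with plamotamab after a tafasitamab infusion reaction.

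- **Section 4.7, Table 8, infusion-related reactions.** The Grade 2 and Grade 3 rows both open with "Interrupt infusion of tafasitamab or plamotamab immediately and manage signs and symptoms", so they cover a reaction to either antibody. Both let the interrupted infusion restart at a slower rate once symptoms have resolved or fallen to Grade 1. Both close with "Dosing of other study medications is not modified". Neither row makes an exception for plamotamab or points to Section 4.6.
- **Section 4.6.2.1 (safety run-in and Part 2 Arm A).** To limit overlapping toxicity, "tafasitamab must be given first with a minimum of 2 hours between the end of the tafasitamab infusion" and the start of plamotamab. It continues: "If a > Grade 1 infusion reaction occurs with tafasitamab, delay the plamotamab until the resolution all symptoms of the reaction". It adds that plamotamab may have to move to the next day.

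The lead-in to Table 8 in Section 4.7 allows sites to manage infusion reactions by their own standard practice and offers Section 4.6 as further guidance. It then presents Table 8 as the detailed, graded instructions for toxicities that could overlap, and names infusion reactions among them. The same section says that a dose delayed for safety is not a protocol deviation.

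**The concern.** The two rules address the same event, at the same grades, in the same patients, and taken at face value they give different instructions. Section 4.6.2.1 makes the start of plamotamab depend on full resolution of symptoms. Table 8 makes it depend on nothing beyond the ordinary schedule.

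What is at stake is patient safety and the clean attribution of early toxicity. Section 4.6 states that the three-drug combination had not been tested in humans. Section 4.6.1.1 wants plamotamab cytokine release syndrome (CRS) kept apart from tafasitamab reactions. Sections 4.6.1 and 4.6.2 list fever, hypotension and dyspnea for both conditions, and the notes to Table 4 require fever, hypotension and hypoxia to have no other cause if they are to count toward the CRS grade. The first day on which both antibodies are given is Cycle 1 Day 1. That is the third tafasitamab infusion, after Days -8 and -4, and the first plamotamab dose, when Section 4.6.1 says CRS is more likely than at later doses.

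**Working it through.** No arithmetic applies, so the check is a comparison of texts.

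**1. Do the two rules cover the same cases?** Section 4.6.2.1 applies above Grade 1, which includes Grades 2 and 3. The Table 8 rows apply to tafasitamab reactions of those grades. They overlap in Part 1 and Arm A on shared dosing days. Arm B receives no plamotamab and is unaffected.

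**2. What does the not-modified wording mean in Table 8?** The table uses it in two ways.

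| Row of Table 8 | What is done to the affected drug | What the wording is set against |
|---|---|---|
| Liver tests, Grade 3 | "Withhold plamotamab and manage signs and symptoms until the toxicity has recovered to" Grade 1 or baseline, with discontinuation if the toxicity persists | a hold or discontinuation |
| Renal impairment, clearance 59-30 mL/min | lenalidomide cut to 10 mg daily | a dose reduction |

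The liver row suggests that an unmodified drug is also not held. The renal row is consistent with a narrower meaning that concerns the amount only. The table does not settle the question.

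**3. Does any text say which rule prevails?** No. Sections 4.6.1.3, 4.7 and 7.10.1 direct the reader to Section 4.6 or 4.6.2, but none ranks those sections against Table 8. Inside the table, the CRS rows do point back, for example "Interrupt plamotamab infusion immediately and manage signs and symptoms (see Section 4.6.1.6", and so does the Grade 3 neurotoxicity row. The infusion-reaction rows do not. Section 4.6.2.2, for Arm B, refers to Section 4.7, whereas Section 4.6.2.1 does not.

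**4. When do the instructions differ in practice?** A gap of at least 2 hours between the antibodies is stated in Section 4.6.2.1, in Section 7.1.1 and in footnote d of Table 9. If all symptoms have gone when that gap ends, both texts allow plamotamab. If any symptom remains, Section 4.6.2.1 says wait and Table 8 states no reason to wait. There are three routes to that situation:

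- Symptoms fall to Grade 1, tafasitamab is resumed and completed, and the residual symptoms outlast the gap. Table 8 allows this sequence; for Grade 3 it reads "Once signs and symptoms resolve or reduce to Grade 1, resume infusion at no more than 25% of the rate" at which the reaction occurred.
- A Grade 3 reaction returns on rechallenge and tafasitamab is stopped. The row still leaves the other drugs unmodified. Only the 2-hour gap then separates the drugs, and symptoms may be above Grade 1.
- The reaction begins after the tafasitamab infusion has ended.

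**5. How often would this happen?** The documents give no rate of tafasitamab infusion reactions and no distribution of symptom duration, so no count of affected patients is offered. Section 4.6.2 says such reactions are most frequent in the first few infusions, and the first two tafasitamab infusions are given without plamotamab.

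**The case against.** The best reply is that the texts can be read together. Table 8 concerns dose modification, Section 4.6.2.1 concerns same-day order and timing, and full-dose plamotamab given some hours later or the next day has not been modified in amount. The renal rows support this reading, and the febrile neutropenia row names dose and schedule separately. Section 4.6.2.1 is also the more specific rule, the lead-in to Table 8 sends the reader to Section 4.6, and a safety delay is not a deviation. Nothing therefore compels an investigator to treat a symptomatic patient.

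Much of this stands. A reader might infer that the Table 8 wording can only mean that the other drugs are not held, which would make the contradiction absolute. The documents do not support that, because the renal rows set the same wording against a dose reduction. A careful investigator who reads both sections would probably delay plamotamab.

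It does not remove the point. The reconciling reading has to be supplied by the reader. The table gives no exception, the liver row uses the same wording against a hold, and Section 4.6 is offered only as additional guidance. Someone working from the table at the bedside is not led to the safeguard.

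A reader might also infer that the Grade 4 row is wrong. It is not. It stops the infusion and permanently discontinues "Tafasitamab if during or immediately following tafasitamab infusion", and it carries no not-modified bullet. It is silent on when plamotamab may be given, and Section 4.6.2.1 already covers that grade.

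**Conclusion.** The inconsistency is real and minor. For Grade 2 and Grade 3 tafasitamab reactions in Part 1 and Arm A, Table 8 states an unqualified rule that, on its natural reading, omits a safeguard the protocol sets elsewhere. The instructions differ on shared dosing days when symptoms persist past the 2-hour gap, including when a Grade 3 reaction returns on rechallenge and tafasitamab is stopped.

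The conclusion rests on reading the table as a site would use it, without an unstated rule that Section 4.6 prevails. Such a rule would reduce the matter to a missing cross-reference.

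A reader might infer that patients were harmed, or that safety or efficacy results were distorted. The documents support neither. They report no case in which the difference mattered, no endpoint, power or error-rate figure depends on it, and the SAP (Sections 1, 4.1 and 7) records early termination with 3 subjects enrolled. The value of the correction lies in any amendment or reuse of this regimen.

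**What to change.** In the Grade 2 and Grade 3 infusion-related reaction rows of Table 8, keep the last bullet, "Dosing of other study medications is not modified", and add to it: except that plamotamab is delayed until all symptoms of a tafasitamab reaction have resolved (see Section 4.6.2.1). The Grade 4 row needs no change to remove the inconsistency.

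The cost is two edited bullets and no new data collection. In use, plamotamab will occasionally be delayed by hours or to the next day. Section 4.6.2.1 already requires that delay, and Section 4.7 already exempts it from being a protocol deviation.
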